4.3 Software

All report outputs will be produced using SAS® version 9.4 or a later version in a secure and validated environment. For quality control of primary endpoint, R version 4.1.1 will be used.

All report outputs will be provided in Microsoft Word document/PDF format.

4.4 Study Patients

4.4.1 Disposition of Patients

A clear accounting of the disposition of all patients who enter the study will be provided, from screening to study completion.

- A summary of the number of patients screened for entry into the study, the number and percentage of patients excluded prior to randomization by major reason and overall, the total number of randomized patients, the total number of patients randomized and treated, the reasons for not being randomized or treated (Enrolled Set)
- A summary of the number of patients randomized per country and site (Randomized Set)
- A summary of the number of patients randomized and treated (with at least one dose of study medication), treated in DB phase, treated in DB and OL phase and the number and percentage of patients withdrawing from study treatment by study phase together with major reason and withdrawing from the study together with major reason by treatment group and overall (Randomized Set).
- A summary of the number and percentage of patients completing each visit of the study by treatment group and overall (Randomized Set).
- Duration of patient participation in the study (Randomized Set).
- A summary of the Covid-19 impact (at least a visit impacted by the Covid-19 pandemic, visits impacted, type of impact to the visits and relationship to Covid-19 during participation to the study) (Randomized Set).

The duration of patient participation will be calculated in days and derived as:

Duration (days) = Date of last visit or last contact – date of informed consent + 1

By-patient listings will be provided.

- Listing of screen failure patients (Enrolled Set)
- Listing of randomization details (Randomized Set).
- Listing of study treatment discontinuation details (including primary reason and study day at discontinuation, whether treatment was unblinded and the last dose date of study treatment) (Randomized Set).
- Listing of study completion or withdrawal details (including primary reason and study day at discontinuation) (Randomized Set).
- Listing of dates of visit including duration of patient participation and Covid-19 impact (Randomized Set).

4.4.2 Protocol Deviations

All protocol violations will be judged as major or minor, taking composite effects of protocol deviations into consideration.

Major protocol deviations are defined as those deviations from the protocol likely to have an impact on the perceived efficacy and/or safety of study treatments. Therefore, patients for whom the clinical outcome is qualitatively affected by the protocol deviations will be excluded.

- Informed consent deviations
- Inclusion/Exclusion criteria deviations
- Disallowed medications
- AEs/SAEs deviations
- IP Administration/ study treatment deviations
- Procedures/tests deviations
- Visit schedule deviations
- Withdrawal criteria deviations

Protocol deviations and any action to be taken regarding the exclusion of patients or affected data from specific analyses are defined in the project-specific Protocol Deviation Specification.

The final classification and effect of each protocol deviation as well as the composite effect of a set of protocol deviations on analysis populations will be assessed prior to the database lock/unblinding on a Blinded Data Review Meeting [BDRM]. Results and population assignments will be summarized in a BDRM report which will be signed off by all relevant scientific experts.

The impact of major protocol deviations on the efficacy and/or safety results will be investigated by assessing the robustness of the study results and conclusions to the choice of analysis set, both including and excluding data potentially affected by major protocol deviations.

The following summaries will be provided:

- A summary of the number and percentage of patients with at least a major protocol deviation and by type of protocol deviation (Randomized Set).

The following listing will be provided:

- All major and minor protocol deviations (Randomized Set).

4.5 Analysis Sets

For purposes of analysis, the following analysis sets are defined:

Population	Description
Enrolled	All patients who signed the ICF (including screening failures).

Population	Description
Randomized	All patients who have been randomized.
Full Analysis Set (FAS)	The full analysis set (FAS) will consist of all patients who have been randomized and received at least 1 dose of IMP. Patients will be analyzed according to randomized treatment (any randomized but not treated patient will be marked and reported as such).
Per Protocol Set (PPS)	The per protocol analysis set (PPS) will consist of all patients who have been randomized and completed the study without any major protocol deviations that are judged to compromise the analysis of the data. Mis-randomized patients will be removed from the PPS. All protocol violations will be judged as major or minor, taking composite effects of protocol deviations into consideration, excluding patients for whom the clinical outcome is qualitatively affected by the protocol deviations.
Safety Analysis Set (SS)	The safety analysis set will consist of all patients who have been randomized and received at least 1 dose of IMP. Patients will be analyzed according to the treatment actually received (in case this differs from randomized treatment).
PK Analysis Set (PKS)	The PK analysis set will consist of all patients who received at least 1 dose of IMP and have at least 1 measurement of plasma concentration of X842/linaprazan. Patients will be analyzed according to the treatment actually received (in case this differs from randomized treatment).

The efficacy summaries and analyses will be based on the **Full Analysis Set**, which is based upon the Intention-to-Treat principle.

For the primary efficacy variable(s), a sensitivity analysis will be performed on the **Per Protocol Set** to assess the robustness of the study conclusions to the choice of analysis population.

Secondary efficacy variable(s) will also be performed on the **Per Protocol Set**.

The PK summaries and analyses will be based on the **PK Analysis Set**.

The safety summaries and analyses will be based on the **Safety Analysis Set**.

Upon database release, protocol deviation and analysis set outputs will be produced and will be sent to Cinclus Pharma for review. An analysis population classification meeting will be arranged to discuss the outputs and to decide which patients and/or patient data will be excluded from certain analysis sets. Decisions made regarding the exclusion of patients and/or patient data from analysis sets will be made prior to unblinding and will be documented and approved by Cinclus Pharma.

The following summary and listing on analysis sets will be provided:

- A summary of the number and percentage of patients in FAS, PPS, Safety Analysis Set and PK Analysis Set by study treatment group and overall and the reason for exclusion from an analysis set (if applicable) (Randomized Set).
- A listing including patient identifier, inclusion/exclusion flag for each analysis set, reason for exclusion from an analysis set (if applicable), randomized and actual study treatment will be provided (Randomized Set).

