4.4 End of Study Definition

All patients who participate in this study and complete Visit 9 (End of Study/Early Termination) visit are considered to have completed the study (Table 1).

The end of the study is defined as the date of the last visit of the last patient in the study.

5 Study Population

Prospective approval of protocol deviations to eligibility criteria, also known as protocol waivers or exemptions, are not permitted.

The patients possibly eligible will be identified as the follows:

1. Patients identified during their routine endoscopy:
 - Patients must have erosive esophagitis identified during the routine endoscopy, before being considered for study screening (prior to signing the ICF).
 - This routine endoscopy will also serve as the index endoscopy in the study and the report should contain the endoscopy findings using the Los Angeles (LA) classification.
 - This routine endoscopy must be obtained within 7 working days of planned randomization, please refer to [Inclusion criterion #4](#).
2. Patients invited for screening upper endoscopy based on their past medical history (both criteria must be met):
 - a) LA grade C or D disease within the past 5 years before screening, demonstrated with endoscopy (endoscopy report issued by a gastroenterologist/endoscopist is accepted)
 - b) In the Investigator's judgement the patient presents clear symptom relapse: patient may be treated with PPI, discontinued PPI treatment (patient's decision) or is being treatment naïve.

For patients invited for screening upper endoscopy, the ICF will be signed prior to the endoscopy. The screening procedures must start with endoscopy and in case the patient doesn't show LA grade C or D erosions, the rest of the screening procedures must not be conducted. This screening endoscopy must be obtained within 7 working days of planned randomization.

The index/screening endoscopy video/digital image will be anonymized and saved for central storage. Imaging data must meet quality standards for adequate LA grading and must be accompanied by a report and videos/digital images to allow retrospective analysis of the endoscopy findings.

Investigators must keep a record of all screened patients even if they were not subsequently randomized in the study. This information is necessary to verify that patients were selected

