9.3 Populations for Analyses

For purposes of analysis, the following analysis sets are defined:

Population	Description
Enrolled	All patients who signed the ICF (including screening failures).
Full Analysis Set (FAS)	The full analysis set (FAS) will consist of all patients who have been randomized and received at least 1 dose of IMP. Patients will be analyzed according to randomized treatment (any randomized but not treated patient will be marked and reported as such).
Per Protocol Set (PPS)	The per protocol analysis set (PPS) will consist of all patients who have been randomized and completed the study without any major protocol deviations that are judged to compromise the analysis of the data. All protocol violations will be judged as major or minor, taking composite effects of protocol deviations into consideration, excluding patients for whom the clinical outcome is qualitatively affected by the protocol deviations.
Safety Analysis Set	The safety analysis set will consist of all patients who have been randomized and received at least 1 dose of IMP. Patients will be analyzed according to the treatment actually received (in case this differs from randomized treatment).

PK Analysis Set	The PK analysis set will consist of all patients who received at least 1 dose of IMP and have at least 1 measurement of plasma concentration of X842/linaprazan. Patients will be analyzed according to the treatment actually received (in case this differs from randomized treatment).
-----------------	---

The FAS will be the primary analysis set for all efficacy analyses and the PPS will be used to demonstrate robustness of results for the primary efficacy endpoint(s).

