Four doses of X842 (25 mg, 50 mg, 75 mg, 100 mg, and dummies) will be administered as tablets twice daily. The active comparator lansoprazole 30 mg and its dummy will be administered as capsules once daily in the morning. The study drugs should be taken with 100 mL of noncarbonated water at least 30 minutes prior to meals. The duration of double-blind treatment will be 28 days -2/+5 days. To blind treatment, each patient will receive 2 tablets (containing doses of X842 or its dummy) and one capsule (containing lansoprazole or its dummy) in the morning and 2 tablets (containing doses of X842 or its dummy) in the evening.

The study design is shown below (Figure 1).

Figure 1 Study Design

The study will comprise 6 visits at the site and 3 telephone visits. Based on the endoscopy findings and/or signed informed consent form (ICF), the screening visit (Visit 1) will take place not more than 7 days prior to randomization and the first dose administration (Visit 2). All patients will then visit the study clinic/investigational site after 7 (Visit 3), 14 (Visit 4) and 28 days (Visit 5) and at the End of Study/Early Termination visit (Visit 9). There are 3 weekly telephone visits after Visit 5. See Table 1 in section 6. All patients who participate in this study and complete Visit 9 (End of Study/Early Termination) are considered to have completed the study (Table 1).

No interim analyses are planned for this study. No data monitoring committees will be used.

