Comparison of different doses of X842 to the active comparator arm (lansoprazole 30 mg) will not involve any formal statistical testing.

Lansoprazole treatment group will be analyzed descriptively.

The primary analysis will be performed for both the FAS and PPS as defined in Section 4.5.

In addition, the two subgroups, erosive esophagitis due to GERD LA grade C or D and erosive esophagitis due to GERD LA grade A or B, will be evaluated separately.

In the subgroup of patients with LA grade A or B, some of them were classified as A or B by investigator and thus are partial responders to PPI, but some of them were initially classified as C or D by investigator, and thus may not be partial responders to PPI. A subgroup analysis will be performed on the subgroup of patients with LA grade A/B according to their history of PPI treatment.

The rate of esophageal mucosa healing in the four X842 dose groups after 4 weeks of treatment (endoscopy performed at Visit 5) will be derived using the LA grading of GERD. If the grading is neither A, B, C or D, then the patient will be considered as having esophageal mucosa healing.

The rate of esophageal mucosa healing will be accompanied by 95% Clopper Pearson CI.

The primary analysis will involve dose-response modeling, evaluating a sequence of dose-response models for the healing rate including the Linear, Exponential, E_{max} , Sigmoid E_{max} and Logistic models (on logit scale).

The models will be compared in terms of model fit, and the target dose estimated as the dose providing the target effect of 85% healing rate from the best fitting model will be derived.

Several dose-response models will be fitted with the following factors:

- randomized study treatment (X842 25mg, X842 50mg, X842 75mg and X842 100mg)
- erosive esophagitis due to GERD (LA grade C or D / LA grade A or B)
- Center

Dose-Response Modeling

Multiple Comparison Procedure – Modeling

For all patients assigned to FAS, dose-response modeling will be performed using the multiple comparison procedure – modeling (MCP-Mod) approach [2, 3] with the following models in consideration:

1. Emax: $f(d) = E_0 + E_{max}d/(ED_{50} + d)$.
2. Sigmoidal Emax with $h = 3.5$: $f(d) = E_0 + E_{max}d^{3.5}/(ED_{50}^{3.5} + d^{3.5})$.
3. Logistic: $f(d) = E_0 + E_{max}/\exp((ED_{50} - d)/\delta)$.
4. Exponential: $f(d) = E_0 + E_1 \exp\left(\frac{d}{\delta}\right)$.
5. Linear: $f(d) = E_0 + \beta * d$.

Where:

- d is the dose level,

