- Estimation of potential target dose based on model-averaging method over all models in the candidate set (FAS subgroup of erosive patients /PPS)

A sensitivity analysis based on local readings will be provided by study treatment group:

- Percentage of patients with esophageal mucosa healing after 4 weeks (Investigator or Endoscopy specialist reading) (FAS)
- Percentage of patients with esophageal mucosa healing after 4 weeks by LA Grade (Investigator or Endoscopy specialist reading) (FAS)

A second sensitivity analysis based on local readings and how those local readings were reclassified by central reading will be provided by study treatment group.

There will be 6 categories:

- Grade C/D that stayed C/D
- Grade C/D reclassified as A/B
- Grade C/D reclassified as grade 0 (non erosive) – if any
- Grade A/B reclassified as C/D – if any
- Grade A/B that stayed A/B
- Grade A/B reclassified as grade 0 (non erosive)

- Percentage of patients with esophageal mucosa healing after 4 weeks by Investigator LA Grade and its reclassification (FAS)

A listing of upper endoscopy results will be provided.

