4.10.3 Secondary Efficacy Variables

Analyses of the secondary efficacy endpoints will be performed for the FAS and the PP as defined in Section 4.5.

QOLRAD scores and mRESQ-eD means or proportions will be estimated using a Generalized Linear Mixed Model (GLMM) approach using information of each week for each subject, on observed data, assuming missing at random.

The models will be implemented using all available timepoints (as categorical), the X842 dose level or lansoprazole as covariate and the related interaction, center and erosive esophagitis due to GERD (LA grade C or D / LA grade A or B).

Toeplitz covariance matrix will be assumed. In case of convergence failure, the following matrices will be tested until convergence is reached: 1. Compound Symmetry, 2. Autoregressive 1 (AR-1).

Mean and standard error estimated from the model will be provided in the outputs. Median, Q1, Q3, Min and Max will be reported as observed data.

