4.3.1.7 Per-Protocol Analysis Set, PPS

[figure not shown]
The PPS will consist of all patients who have been randomized and completed the study without any major protocol deviations that are judged to compromise the analysis of the data. Mis-randomized patients will be removed from the PPS. All protocol violations will be judged as major or minor, taking composite effects of protocol deviations into consideration, excluding patients for whom the clinical outcome is qualitatively affected by the protocol deviations.

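### The per-protocol check on week-4 healing requires attendance at Visit 9, so a patient with a valid Visit 5 endoscopy can be excluded for something that happened after the outcome

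*SAP*

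**What the plan says.** SAP section 4.5 builds the PPS from patients who were "randomized and completed the study without any major protocol deviations" judged to compromise the analysis. Protocol section 9.3 has the same definition. SAP amendment 01, section 4.3.1.7, keeps the condition: "all patients who have been randomized and completed the study without any major protocol deviations".

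Completion has its own definition. SAP section 3.1 says that patients who "complete Visit 9 (End of Study/Early Termination) are considered to have completed the study", and Protocol sections 4.4 and 10.2.6 agree. The schedule of assessments puts Visit 9 at Day 56 ±3 days and Visit 5 at Day 28 -2/+5 days. SAP section 4.10.2 derives healing from the Visit 5 endoscopy.

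The PPS is the named robustness check on healing (Protocol 9.3, SAP 4.5), called supportive in section 4.5.2 of the amendment. SAP section 4.10.2 repeats the MCP-Mod tests and the target-dose estimate on it. The same set also serves endpoints that run to week 8: "Analyses of the secondary efficacy endpoints will be performed for the FAS and the PP as defined in Section 4.5".

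**The concern.** A per-protocol analysis of week-4 healing should differ from the full-analysis result because of eligibility and adherence up to the week-4 endoscopy. Requiring Visit 9 adds a condition that can be met only after healing status is fixed, during a period when every arm takes open-label lansoprazole. If attendance in that period is related to whether the patient healed, the PPS healing rate shifts for a reason unrelated to protocol adherence. A gap between the PPS and FAS erosive could then be misread as an effect of deviations, or a real effect of deviations could be masked. The PPS target-dose output would carry the same selection.

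**Working it through.** **The definitions side by side.** There is no stated figure to reproduce: the sample-size sections are redacted and the point rests on no power calculation.

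1. PPS membership requires completing the study (Protocol 9.3; SAP 4.5; amendment 4.3.1.7).
2. Completing the study means completing Visit 9 (Protocol 4.4 and 10.2.6; SAP 3.1).
3. Gap from Visit 5 to Visit 9: 56 − 28 = 28 days nominally. Across the visit windows it runs from (56 − 3) − (28 + 5) = 20 days to (56 + 3) − (28 − 2) = 33 days.
4. The qualifier about compromising the analysis attaches to deviations, not to completion. No visible text waives completion for week-4 healing.

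**Who is affected.** Patients who stop early are scheduled for the termination visit 4 weeks after stopping treatment (Protocol 4.2, SAP 1), and that visit counts as Visit 9. Protocol 7.4 requires contact attempts up to the time of Visit 9. Protocol 7.2, however, has withdrawn patients seen only where possible. What remains is patients with a Visit 5 endoscopy and no Visit 9 at all, for example those lost to follow-up or withdrawing consent.

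**Size per arm.** The number affected is not in the documents, so these are illustrations. Planned evaluable patients per arm: 200/5 = 40. Assume 34 healed: 34/40 = 85.0%, 95% Clopper-Pearson interval 70.2–94.3%.

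| Lost from the arm | PPS rate | Shift (points) |
|---|---|---|
| 1 unhealed | 34/39 = 87.2% | +2.2 |
| 1 healed | 33/39 = 84.6% | −0.4 |
| 2 unhealed | 34/38 = 89.5% | +4.5 |
| 2 healed | 32/38 = 84.2% | −0.8 |

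**Size by rate of non-attendance.** Let p = 0.85, with d_h and d_u the assumed proportions of healed and unhealed patients who miss Visit 9. The PPS rate is p(1 − d_h) / [p(1 − d_h) + (1 − p)(1 − d_u)].

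| d_h | d_u | PPS rate |
|---|---|---|
| 5% | 5% | 85.0% |
| 2.5% | 7.5% | 85.7% |
| 2.5% | 12.5% | 86.3% |
| 5% | 15% | 86.4% |
| 5% | 25% | 87.8% |
| 15% | 5% | 83.5% |
| 25% | 5% | 81.7% |

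Equal loss in healed and unhealed patients gives no shift.

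**Size for a target-dose estimate.** Assume 26, 30, 33 and 36 of 40 healed at 25, 50, 75 and 100 mg, and fit an unadjusted logistic model linear in dose. The intercept is a = 0.0923 and the slope b = 0.02032. The 85% point is (logit(0.85) − a)/b = (1.7346 − 0.0923)/0.02032 = 80.8 mg, with a 95% Fieller interval of 61.2–156.1.

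| Lost | 85% point (mg) | Shift |
|---|---|---|
| 1 unhealed, top arm | 76.4 | −4.4 |
| 1 healed, top arm | 81.4 | +0.6 |
| 1 unhealed, every X842 arm | 72.3 | −8.5 |
| 1 healed, every X842 arm | 82.3 | +1.5 |

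Every shift lies inside the interval. The counts are invented and the model is simpler than the planned MCP-Mod with bootstrap and covariates. The figures show only how a fit of this kind responds to single patients, and no dose is implied.

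**The case against.** The strongest reply is that nobody may be affected. The Protocol Deviation Specification cited in SAP 4.4.2 is not among these documents, and it or the population meeting before unblinding (SAP 4.5) may have dealt with such cases. The figure legend in section 4.3 of the amendment places the whole PPS inside mFAS erosive, the week-4-evaluable set. The written PPS definition names no endoscopy, so other rules evidently shaped membership. A missed Visit 9 might also have been classed as a major visit-schedule deviation, in which case changing the completion wording would bring no patient back. All of this stands as uncertainty about what was done. None of it changes the written rule.

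A second reply is that healing is already summarised on mFAS erosive, which has no Visit 9 condition. That is true, but mFAS erosive is not filtered for deviations, so it does not replace a per-protocol analysis.

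A third is that one PPS serves both week-4 and week-8 endpoints. That can explain a week-8 condition for the symptom endpoints. It does not justify one for healing.

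Finally, the worked examples rest on assumed counts and all their shifts are small beside the sampling error. This is correct, and it is why the point is minor.

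**Conclusion.** The concern holds for the definition as written: the supportive PPS analysis of week-4 healing is conditioned on attendance 20 to 33 days after the outcome is read. It is a minor point. The number affected is unknown and may be zero, the direction of any bias cannot be stated, and the primary analysis on FAS erosive is untouched. Under the assumed 34 of 40 healed, one lost patient moves an arm's rate by between −0.4 and +2.2 points, well within its confidence interval. The conclusion assumes that completion was applied literally. Whether any valid Visit 5 result was actually discarded cannot be settled from these documents.

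**What to change.** In the definition, and for healing only, replace study completion with having a graded Visit 5 endoscopy. Leave the other PPS criteria, and the deviation classifications made before unblinding, as they are. Keep the Visit 9 condition only for summaries that use weeks 5–8.

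For this trial the data are already unblinded (amendment section 3), so the pre-specified PPS result should stay as reported. Beside it, give the number of patients excluded from the PPS solely for missing Visit 9, by arm and by healing status. If it is zero, say so and stop. If it is not, repeat the healing PPS analysis with those patients included, labelled post hoc and supplementary.

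The cost is one cross-tabulation from outputs already planned: visit completion by arm and the withdrawal listings (SAP 4.4.1), reasons for exclusion from each set (SAP 4.5, amendment 4.4) and the endoscopy listing (SAP 4.10.2). At most one further exploratory analysis follows, in a results hierarchy that already has three levels. No deviation is re-classified.
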